## PROTOCOL SUMMARY

**Protocol number:** CSOM230GUS44T

**Title** PILOT STUDY OF PASIREOTIDE LAR TREATMENT OF SILENT CORTICOTROPH PITUITARY TUMORS AND EFFECTS ON PLASMA LEVELS OF POMC

**Clinical Phase:** Phase II

**Investigation Type:** Drug

**Study Type:** Interventional

**Purpose and Rationale:** The purpose of this trial is to test the main hypotheses that Pasireotide LAR treatment of patients with silent corticotroph pituitary tumors and elevated or normal plasma POMC levels will reduce plasma POMC levels and this will be associated with a reduction in pituitary tumor size.

**Primary Objective:** To determine the efficacy of Pasireotide LAR to suppress plasma levels of POMC in patients with silent corticotroph pituitary tumors.

**Secondary Objectives:** To determine the effect of Pasireotide LAR therapy on pituitary tumor volume in patients with silent corticotroph pituitary tumors.

**Study design:** This is an open-label, 12-month pilot study of Pasireotide LAR therapy of 10 patients with silent corticotroph pituitary tumors. Pasireotide LAR 40 mg will be administered monthly. Baseline and monthly visits on therapy will monitor plasma levels of POMC, other pituitary function, safety labs, glucose tolerance, physical examination, and visual fields. Pituitary MRI will be done at baseline, 6 months and 12 months of therapy. The starting dose is Pasireotide LAR 40 mg/month given as intramuscular injection. The dose will be increased to 60 mg/month at 6 months if a fall in POMC levels and/or tumor shrinkage are not attained. LAR will be administered monthly with the last injection at Week 44.

**Study Population:** The eligible patient population will consist of adult patients with known silent corticotroph pituitary tumors and elevated or normal plasma levels of POMC.

**Key Inclusion criteria:**

Subjects must meet all of the following inclusion criteria to be eligible for enrollment into the study:

- Adults (males and females, ages 18-70 years) with a diagnosis of a clinically nonfunctioning pituitary tumor of the silent corticotroph tumor type (i.e. positive ACTH staining on immunohistochemical staining of the pituitary tumor obtained at surgery)
- Plasma POMC level within or greater than the upper limit of normal

- Prior pituitary tumor surgery with residual or recurrent pituitary tumor visible on MRI scan that is  $\geq 5$  mm from the optic chiasm
- Surgical resection of the pituitary adenoma must have occurred two or more months prior to the baseline visit.
- If patients have undergone pituitary radiotherapy they must have completed their course of radiotherapy at least 2 months prior to study screening
- No prior somatostatin analog therapy
- No concurrent use of dopamine agonist therapy
- No active malignancy
- Stable pituitary hormone supplements (x 2 months) prior to baseline visit
- Sign and date an informed consent document indicating that the subject has been informed of and agrees to all pertinent aspects of the trial

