#### 3.2 Study population

Ten (10) patients with clinically nonfunctioning pituitary tumors of the silent corticotroph tumor subtype will be studied in this protocol. Males and females are eligible for enrollment. Subjects ages 18 – 80 are eligible for enrollment. Patients will be drawn from primarily from our cohort of 285 patients with clinically nonfunctioning pituitary tumors followed in our prospective study. Patients will also be recruited from subjects treated at our Neuroendocrine Unit and Pituitary Center for who are known to have silent corticotroph pituitary tumors. The investigator will ensure that only patients who meet all

the following inclusion and none of the exclusion criteria are offered treatment in the study. The investigator will maintain an enrollment log of screened/enrolled subjects.

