### **3.2.1 Inclusion and exclusion criteria**

#### **Inclusion criteria:**

Subjects must meet all of the following inclusion criteria to be eligible for enrollment into the study:

1. Adults (males and females) (ages 18- 80 years) with a diagnosis of a clinically nonfunctioning pituitary tumor of the silent corticotroph tumor type (i.e. positive ACTH staining on immunohistochemical staining of the pituitary tumor obtained at surgery)
2. Plasma POMC level within or greater than the upper limit of normal
3. Prior pituitary tumor surgery with residual or recurrent pituitary tumor visible on MRI scan that is  $\geq 5$  mm from the optic chiasm.
4. Surgical resection of the pituitary adenoma must have occurred two or more months prior to baseline visit.
5. If patients have undergone pituitary radiotherapy they must have completed their course of radiotherapy at least 2 months prior to study screening
6. No prior somatostatin analog therapy
7. No concurrent use of dopamine agonist therapy
8. No active malignancy
9. Stable pituitary hormone supplements (x 2 months) prior to baseline visit
10. Sign and date an informed consent document indicating that the subject has been informed of and agrees to all pertinent aspects of the trial

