#### **Exclusion criteria**

Subjects must not meet any of the following exclusion criteria to be eligible for enrollment into the study:

1. Patients with Cushing's disease (biochemical evidence of hypercortisolism).
2. Patients with compression of the optic chiasm causing any visual field defect that requires surgical intervention
3. Diabetic patients with poor glycemic control as evidenced by HbA1c  $>8\%$
4. Patients who are hypothyroid or adrenally insufficient and not on adequate replacement therapy
5. Patients with symptomatic cholelithiasis and acute or chronic pancreatitis
6. Patients with risk factors for torsade de pointes, i.e. patients with a baseline QTcF  $>450$  ms in males, and  $>460$  ms in females

7. Hypokalaemia, hypomagnesaemia, uncontrolled hypothyroidism, family history of long QT syndrome or concomitant medications with known risk of Torsades de pointes (TdP). Drugs with possible risk of TdP should be avoided whenever feasible.
8. Patients who have congestive heart failure (NYHA Class III or IV), unstable angina, sustained ventricular tachycardia, clinically significant bradycardia, advanced heart block, history of acute MI less than one year prior to study entry or clinically significant impairment in cardiovascular function
9. Concomitant disease(s) that could prolong the QT interval such as autonomic neuropathy (caused by diabetes or Parkinson's disease), HIV, cirrhosis, uncontrolled hypothyroidism or cardiac failure
10. Patients with liver disease such as cirrhosis, chronic active hepatitis, or chronic persistent hepatitis, or patients with ALT/AST > 2.0 X ULN, serum bilirubin >2.0 X ULN
11. Presence of Hepatitis B surface antigen (HbsAg) or Hepatitis C antibody test (anti-HCV)
12. Patients with serum creatinine >2.0 X ULN
13. Patients with WBC <3 X 10^9/L; Hb 90% < LLN; PLT <100 X 10^9/L
14. Patients with the presence of active or suspected acute or chronic uncontrolled infection
15. Patients who have undergone major surgery/surgical therapy for any cause within 4 weeks prior screening
16. Patients with abnormal coagulation (PT and/or APTT elevated by 30% above normal limits) or patients receiving anticoagulants that affect PT (prothrombin time) or APTT (activated partial thromboplastin time)
17. History of syncope or family history of idiopathic sudden death
18. History of immunocompromise, including a positive HIV test result (ELISA and Western blot)

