### 3.3.2. Concomitant therapy

Chronic maintenance medications will continue on their current therapy during the course of the study. The patient will be told to notify the investigational site about any new medications he/she takes after the start of the study drug. Any changes in the dose of any medication the patient was taking prior to or during the study have to be notified as well. All medications (other than study drug) and significant non-drug therapies (including physical therapy and blood transfusions) administered during the study will be documented in the subject records.

The use of drugs that may stimulate GH secretion such as L-dopa or arginine is not permitted. In addition, the use of the drugs listed in the exclusion criteria is not permitted.

Limited published data indicate that somatostatin analogs might decrease the metabolic clearance of compounds known to be metabolized by cytochrome P450 enzymes, which may be due to the suppression of growth hormones. Since it cannot be excluded that pasireotide may have this effect, other drugs mainly metabolized by CYP3A4 and which have a low therapeutic index (e.g., quinidine, terfenadine) should therefore be used with caution. Consumption of fruits that may inhibit the CYP3A4 system (star fruit, papaya, pomegranate and grapefruit) will also be advised against during the study.

Somatostatin analogs have been associated with alterations in nutrient absorption, so pasireotide may have an effect on absorption of orally administered drugs. Concomitant administration with cyclosporine may decrease blood levels of cyclosporine and result in transplant rejection.

Patients receiving insulin, oral hypoglycemic agents, beta-blockers, calcium channel blockers, or agents to control fluid and electrolyte balance, may require dose adjustments of these therapeutic agents. Any anti-diabetic medications that the patient takes during the study will be listed in study-specific source documents. If oral contraception is used, the patient must have been practicing this method of birth control for at least three months prior to enrollment and must agree to continue the oral contraceptive throughout the course of the study and for 3 months after pasireotide LAR last dose.

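### The Protocol Summary and section 3.2.1 set different entry rules (upper age 70 versus 80; two exclusions only in the summary), and section 3.3.2 offers two drugs on the torsades-risk list as examples for cautious use

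*Combined protocol and SAP*

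**What the plan says.** **Age.** The Key Inclusion criteria in the Protocol Summary open with "Subjects must meet all of the following inclusion criteria to be eligible for enrollment into the study", and the first item is "Adults (males and females, ages 18-70 years". In the body, section 3.2 has "Subjects ages 18 – 80 are eligible for enrollment", and criterion 1 of section 3.2.1 has "Adults (males and females) (ages 18- 80 years". Section 3.2 sends the investigator to the list in section 3.2.1: only patients who meet all "the following inclusion and none of the exclusion criteria are offered treatment in the study".

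**Exclusions.** The summary lists ten key exclusions. Section 3.2.1 lists 21 numbered ones, introduced as conditions that no enrolled patient may meet.

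**Drugs.** Exclusion 7 covers "concomitant medications with known risk of Torsades de pointes (TdP". Section 3.3.2 adds that "the use of the drugs listed in the exclusion criteria is not permitted". Under its subheading on prohibited medication, it bans drugs with a known torsades risk, requires the study drug to be discontinued before one is started, and refers to Appendix 1. The paragraph of the same section on CYP3A4 metabolism says that other drugs with a low therapeutic index "e.g., quinidine, terfenadine) should therefore be used with caution".

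**The concern.** Entry criteria have to give one answer for each patient. Here a 75-year-old fails the summary list and passes the body list, so whether enrolling that patient is a protocol deviation depends on the page consulted. Screening from section 3.2.1, as section 3.2 directs, leaves two exclusions that appear only in the summary unapplied.

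The drug passages raise the same difficulty during treatment. One paragraph describes cautious use of two named agents, while the prohibition a little further on requires study drug to stop before either is started. QT prolongation is among the adverse reactions reported in section 1.2.1.1, and section 3.4.2 has detailed QT monitoring rules, so the ambiguity falls on a risk that the protocol itself treats as important.

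**Working it through.** The plan has no figure to reproduce on this point. The check is a comparison of passages, all in current text.

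**Step 1: inclusion lists.** The Protocol Summary has 10 items and section 3.2.1 has 10. Matched one to one, 9 agree in substance and 1 differs, the upper age limit. Because every item is carried over, abbreviation does not explain the difference.

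| Place | Age range |
|---|---|
| Protocol Summary, Key Inclusion criteria | 18 to 70 |
| Section 3.2 | 18 to 80 |
| Section 3.2.1, criterion 1 | 18 to 80 |

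The band in conflict is ages 71 to 80. The documents give a source cohort of 285 patients but no age distribution, so the number affected cannot be derived. With 10 patients planned, each enrolled patient is 1/10 = 10% of the sample.

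**Step 2: exclusion lists.** Each summary item was set against exclusions 1 to 21.

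| Summary item (paraphrased) | Nearest numbered exclusion | Result |
|---|---|---|
| Cushing's disease | 1 | Match |
| Need for surgery, unqualified | 2: chiasm compression with a field defect needing surgery | Summary wider |
| HbA1c above 8% | 3: same threshold, worded for diabetic patients | Counterpart present |
| Hypersensitivity to the drug class | None | Summary only |
| Past liver disease | 10: named existing disease and laboratory limits (9 and 11 also bear on this) | Summary wider |
| Gallstones or pancreatitis | 5: joined by *and* where the summary has *or* | Counterpart present |
| Cardiac or repolarization problem | 6 to 9 | Counterpart present |
| Life-threatening autoimmune disease | None; 18 concerns immunocompromise and HIV | Summary only |
| Undertreated adrenal or thyroid deficiency | 4 | Match |
| Poor marrow function | 13 | Counterpart present |

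Two of 10 have no counterpart, and at least 2 more are wider than the body. The numbering in section 3.2.1 runs unbroken from 1 to 21, so removed pages do not explain the two absent items. A list headed as key criteria may reasonably be shorter than the full list, but it should not hold exclusions that the full list lacks.

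**Step 3: drugs.**

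- The CYP3A4 sentence in section 3.3.2 names two examples, quinidine and terfenadine.
- The prohibition in the same section covers drugs with a known torsades risk and refers to Appendix 1.
- The sentence directly above the Appendix 1 list describes its contents as drugs generally accepted to carry a torsades risk.
- Quinidine and terfenadine are both on that list, so 2 of 2 examples for cautious use fall under the prohibition.

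**The case against.** The strongest reply is that the body governs. Section 3.2 directs the investigator to section 3.2.1, the body gives 80 twice, and the summary's exclusion list, unlike its inclusion list, has no binding lead-in, only a heading marking the items as key. This is fair, and it means that the two exclusion lists do not carry equal force. But no passage says that the body overrides the summary, and the summary's inclusion list does carry the binding sentence. If the body does govern, the two summary-only exclusions are simply not applied.

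Short labels are also naturally wider than full criteria. For liver disease in particular, exclusion 11 (hepatitis B and C markers) and the mention of cirrhosis in exclusion 9 narrow the gap. The surgery and liver points are therefore minor. The summary is still literally wider on both.

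Hypersensitivity to the class would usually follow exposure, which inclusion criterion 6 bars, and section 3.3.2 discontinues anyone who develops an allergic reaction to study drug. That reduces the practical gap for hypersensitivity but leaves the autoimmune exclusion untouched.

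On the drugs, the caution sentence describes a class and is not an explicit permission, and a site following the prohibition breaches nothing. Appendix 1 also opens by speaking of a possible association with QT prolongation, whereas exclusion 7 treats known and possible risk differently. That ambiguity is real. However, the sentence immediately above the list speaks of torsades risk, and the prohibition refers the reader to this appendix, so the two examples still conflict with it.

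Finally, this is a 10-patient study drawn mainly from one unit's own patients under a sponsor-investigator, which makes confusion between independent sites less likely. That bears on how serious the problem is, not on whether the text is consistent.

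**Conclusion.** The concern holds: the text is wrong as written and should be corrected. The age limit is the clearest part, a direct numerical contradiction (70 in one place, 80 in two) that leaves eligibility at ages 71 to 80 undetermined. Next come the two exclusions found only in the summary. The surgery and liver wording and the two drug examples are smaller matters of drafting, though the drug examples bear on safety.

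The conclusion assumes that no precedence rule exists between summary and body, since none is stated, and that Appendix 1 is the list meant by the prohibition. No effect on power, sample size or analysis is claimed. The number of patients affected cannot be established from the documents.

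**What to change.** Make one wording amendment that:

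- states a single upper age limit in the Protocol Summary, section 3.2 and criterion 1 of section 3.2.1;
- aligns the summary and section 3.2.1 exclusion lists item by item, covering hypersensitivity, life-threatening autoimmune disease, need for surgery and liver disease;
- reconciles the status of quinidine and terfenadine across exclusion 7, both parts of section 3.3.2 and Appendix 1.

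Which age limit, exclusion wording or drug rule applies is for the sponsor-investigator to decide. Section 5.1 requires IRB approval of the amendment. It changes nothing in the sample size, visit schedule or analysis.

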#### Key Exclusion criteria

- Patients with Cushing's disease (biochemical evidence of hypercortisolism)
- Patients who require surgical intervention.
- HbA1c  $> 8\%$  at screening
- Known hypersensitivity to somatostatin analogues
- History of liver disease
- Symptomatic cholelithiasis or acute or chronic pancreatitis
- Cardiac or repolarization abnormality
- Life-threatening autoimmune disorders
- Inadequately treated adrenal or thyroid insufficiencies
- Inadequate bone marrow function

**Investigational therapy:** Pasireotide LAR

#### **Efficacy assessments**

Primary efficacy parameter: Change in plasma POMC levels from baseline to 12 months of Pasireotide LAR treatment.

Secondary efficacy parameter: Change in pituitary tumor volume from baseline to 12 months of Pasireotide LAR treatment.

#### **Safety assessments**

- Adverse Events
- Laboratory evaluations
- Cardiac assessments (ECG)
- Vital Signs
- Blood glucose monitoring
- Gall bladder ultrasound
- Pituitary MRI

## 1 BACKGROUND

### 1.1 Overview of disease pathogenesis, epidemiology and current treatment

#### Silent Corticotroph Pituitary Adenomas

Clinically non-functioning pituitary adenomas (CNFAs), the subtype of pituitary adenomas that does not appear to secrete biologically active hormone nor to have a characteristic clinical phenotype, are the most common type of pituitary macroadenoma at diagnosis. Many CNFAs are of gonadotroph cell origin (1), but some CNFAs are of corticotroph cell origin (2). These “silent” corticotroph adenomas show adrenocorticotrophic hormone (ACTH) by immunohistochemistry, but do not secrete biologically active ACTH and thus do not have biochemical evidence of cortisol excess or produce a clinical syndrome of glucocorticoid excess (3). Although typically categorized as a type of nonfunctioning pituitary tumor, such silent corticotroph adenomas seem to be at one end of the spectrum of the ACTH producing pituitary tumors that produce clinical Cushing’s disease (CD). Some data suggest that the cell of origin of the silent corticotroph tumor cell is a corticotroph progenitor cell (4). Other data also suggest that there may be dysfunctional processing of pituitary hormones within the cells of silent corticotroph tumors (5-7). This is supported by the findings that increased amounts of mRNA of the ACTH precursor POMC have been measured in silent corticotroph tumors (8-10). ACTH derives from a pro-opiomelanocortin (POMC) precursor, that is cleaved at the C-terminal of ACTH by prohormone convertase (PC) 1, to give rise to  $\beta$ -LPH and pro-ACTH.  $\beta$ -LPH and pro-ACTH are further cleaved into N-terminal POMC, joining peptide (JP) and ACTH, prior to additional processing by PC2 and post-translational modification. The extent of POMC processing varies from tissue to tissue, and in ACTH dependent Cushing’s syndrome, POMC processing appears to depend on the degree of tumor cell differentiation. Data from early chromatographic studies suggests that ectopic ACTH-producing tumors secrete high molecular weight ACTH precursors. Other data, including a recent study conducted by our co-investigator, [name], have found that patients with ectopic ACTH tumors have higher levels of ACTH precursors, reflecting decreased POMC processing, than patients with Cushing’s disease (11-14). Elevations of POMC precursors have been found in some patients with silent corticotroph adenomas (15-17), consistent with the less differentiated state of the tumor cells.

There is currently no option for medical therapy of CNFA, in general, or specifically of silent corticotroph tumors. Silent corticotroph tumors can range from being completely asymptomatic to becoming large and causing significant hypothalamic/pituitary dysfunction and visual symptoms, and most data support that this type of tumor has a more aggressive phenotype (10,18,19). Current therapy consists primarily of surgical removal of the tumor and for recurrent or residual tumors, repeated surgery and/or radiotherapy. In very aggressive tumors, chemotherapy has been tried with some success (20). Therefore, a need exists for a medical therapeutic option for the treatment of this tumor type. This project assesses this clinical need.

This protocol is a pilot study of the efficacy of Pasireotide LAR for the treatment of silent corticotroph pituitary tumors that have elevated plasma levels of POMC. We hypothesize that elevated plasma POMC levels will be a marker for this tumor type and the response of this tumor type to Pasireotide LAR therapy.

### 1.2 Introduction to Investigational Treatment

Somatostatin is an endogenous peptide that modulates a number of exocrine and endocrine secretions. Pasireotide is a somatostatin analog (SSA) with a broader somatostatin receptor binding profile relative to currently available somatostatin analogs (e.g., octreotide, SMS 201-995, Sandostatin®). Pasireotide LAR (Brand name SIGNIFOR LAR) is a somatostatin analog indicated for the treatment of patients with acromegaly who have had an inadequate response to surgery and/or for whom surgery is not an option. Pasireotide LAR (SIGNIFOR® LAR) is a long acting release injectable suspension for intramuscular use. It was approved in the U.S. in 2012 for the treatment of acromegaly. Pasireotide is also available in a short acting subcutaneously administered from which is approved for the treatment of Cushing's disease. As of the cut-off date of April 24, 2015, Pasireotide (Brand name Signifor®) as subcutaneous formulation has been granted marketing authorization in more than 75 countries and pasireotide as long-acting depot formulation in more than 30 countries worldwide. Pasireotide LAR is also being studied for the treatment of patients with Cushing's disease, neuroendocrine tumors (NET), and dumping syndrome.

